THE EFFECT OF THERAPEUTIC TOUCH AND MUSIC REST ON SLEEPING APPLIED TO CHILDREN WITH LIVER TRANSPLANTATION

ID: TDK-2020-2358

NCT ID not yet assigned

Initial Release: 09/09/2021

MATERIAL AND METHOD

Desing of Research

The research was planned as a quasi-experimental study.

Place and Time of Research

The research will be carried out at İnönü University Turgut Özal Medical Center Liver Institute Pediatrics Clinic between February 2021 and October 2021. Pediatric transplant patients are followed in the 19-bed pediatric clinic of the institute.

Population and Sample of the Research

The population of the research will be children between the ages of 0-18 who had liver transplantation at İnönü University Turgut Özal Medical Center Liver Institute between February 2021 and October 2021 and were hospitalized in the pediatric clinic of the institute. The number of patients to be included in the study was calculated as 50 when the calculation was made by taking the confidence interval of 95% in the sample whose population is known. Of the 50 patients sampled, 24 will be included in therapeutic touch groups and 24 in music concert groups.

Randomization:

Assignment of the participants to the control and experimental groups will be done by stratification and block randomization method. Children will be stratified according to their age (0-1, 2-5, 6-12, 13-18 years) and randomization with blocks will be made. In order to prevent bias, children who were stratified were assigned to the control and experimental groups by drawing lots. The research groups will be written on separate papers and the group will be

determined by drawing lots during data collection. In this way, the number of children included in the groups and the probability of each child to be included in the study in the experimental or control group will be equalized.

Inclusion criteria:

*Being within a period of at least one month and at most two years after the transplant

* 0-18 years old

* Conscious

*spontaneous breathing

*No hearing problems

*Pain free

*Children who do not use sleeping pills will be included in the study.

Data Collection Tools

The data will be collected by face-to-face interview technique with the "Introductory Information Form", "Actigraphy" created by the researcher between February 2021 and October 2021.

Introductory Information Form

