The "Introductory Information Form", prepared by the researcher in line with the literature, consists of a total of 15 questions such as the age, gender, education status of the child and parent, and the time of transfer.

Actigraphy

Actigraphy measures the sleep and wake cycles of children and adolescents, detects motor activities with precision, is worn on wrists or ankles, and allows for recording and storing resting and activity patterns in a digital environment; small, lightweight, portable device in the form of a watch (Ertan & Alkan, 2012). The actigraphy device, which can be easily attached to the wrist of the patients, is used to evaluate and document the physical movements of the patients related to sleep. The device can keep a record of the patient's activity for 24 hours. The patient's information can be read and evaluated with the help of a special software of the device.

Data Collection

Data will be collected through face-to-face interviews with children aged 0-18 years, who had liver transplantation at İnönü University Turgut Özal Medical Center Liver Institute and were hospitalized in the pediatric clinic of the institute. The study will consist of therapeutic touch group and music groups. Which group the participants will be in will be determined by drawing lots. One of the experimental groups will be treated with therapeutic touch, and the other will be listened to a music preferred by the family/child. In both groups, children's sleep will be evaluated with pre-test, post-test and follow-up applications. In this study, applications to the "Therapeutic touch" and "music" groups will be done once a day (morning or afternoon) for three days, in the form of a 15-20 minute application period. Children's sleep will be evaluated with "Actigraphy" the day before the application, the day the application ends, and the fourth day after the application.

Intervention Materials

Therapeutic Touch:

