Therapeutic touch; It is a low-cost, non-contra-indications, easy-to-apply and non-invasive form of complementary therapy that can be applied anywhere and at any time (Vanaki et al., 2016). Therapeutic touch was developed by Krieger in 1975 as a nursing intervention to help and even heal the patient by balancing the patient's energy field (Marta et al., 2010). The basic assumption of therapeutic touch is that people have energy fields and these energy fields interact with the environment (Hanley, 2008). Therapeutic touch aims to harmonize, renew and heal the flow of the human energy field by removing the blockages of a person's biofield (Mueller et al., 2019). Unlike other touch-based methods such as massage therapy, therapeutic touch does not require the practitioner to physically touch the patient. Instead, the practitioner uses their hands to focus their energy and intent to help the recipient (Hanley, 2008).

In order to practice therapeutic touch, the researcher attended a certified course organized by the "Therapeutic Touch Association" and received a post-course certificate.

Music Rest:

The use of music in the treatment of diseases has been seen in many civilizations since ancient times. In ancient Greek and Roman communities, individuals resorted to music to get rid of their humanitarian problems, while in Ancient Egypt, music was used to give strength to patients during birth (Kor & Adar, 2016). In today's studies, it has been determined that music positively affects the physiological parameters, nutrition, hospital stay and sleep of the patients (O'Toole et al., 2017; Van Der Heijden et al., 2016). It is important that the sound level is within

the appropriate limits while listening to music to the patients. The American Academy of Pediatrics recommends a sound level between 45dB- a maximum of 65dB (ACOG - AAP, 2012). The World Health Organization recommends a sound level of 35 dB during the day and 30 dB at night (Berglund et al., 2000). In this study, a music (such as lullaby, classical music) preferred by the patient or his family will be played to the children for 20 minutes once a day (morning or afternoon) for three days to help the child sleep. The sound level of the music played will be kept between 45-65 dB.

Nursing Initiative

In this study, the effects of "Therapeutic Touch" and "Music Concert", which are nursing practices, on the sleep of children who have been transferred will be compared.

Therapeutic Touch Group:

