*Parents and children will be informed about "Therapeutic Touch", which is an easy-to-apply and non-invasive application before the procedure.

*One day before starting the "Therapeutic Touch" application, the child's sleep will be evaluated with "Actigraphy". Starting the day after the first measurement, "Therapeutic Touch" will be done in the form of a 20-minute daily application period for three days.

* Before the "Therapeutic Touch" application, the patient's room will be ventilated and a spacious and quiet environment will be provided during the application.

TD process:

*After the procedure was explained, the focus was on the child to be treated,

*Intended to help the child's treatment and sleep,

*The patient's energy field was scanned with the hands at a distance of 8-12 cm from the patient's skin (2 times)

*To remove the blockages determined regarding the energy flow and to facilitate the energy flow, manual cleaning was performed (2 times),

*Imbalances in the energy fields were tried to be treated by using mental visualization techniques such as dreaming, positive thinking and visualization, by directing the universal life energy to sick individuals with calm and rhythmic hand movements (2 times),

*Reassessed to determine whether success has been achieved in treating imbalances in the energy field.

Music Rest Group:

*Parents and children will be informed about the “Music Rest” before the procedure.

*One day before the “Music Rest” practice, the child's sleep will be evaluated with “Actigraphy”. Starting the day after the first measurement, the “Music Rest” will be held for three days as a 20-minute practice period per day. In order to help the child sleep, the child will be listened to music (such as lullaby, classical music) preferred by the patient or his family.

*Before the “Music Rest” application, the patient's room will be ventilated and a spacious and quiet environment will be provided during the application.

*The sound level of the music played will be kept between 45-65 dB.

*Nursing interventions will be written in more detail after the data of the research is collected.

Variables of the Study

Dependent variables: “Actigraphy”

Independent variables: Therapeutic touch, recital

Control variable: Age, gender, height, weight, place of residence, economic status, pain

Evaluation of Research Data

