IBM SPSS Statistics 25.0 package program will be used in the evaluation of the research data. Percentage, mean, standard deviation, normal distribution, t-test in independent groups, t-test and ANOVA tests in dependent groups, multiple linear regression and correlation analyzes will be used in the evaluation of the data. Statistical significance level will be accepted as $p<0.05$.

Ethical Principles of Research

Before the study, children and their parents will be included in the study after an explanation is given about the study and their written and verbal consents are obtained. Ethics committee approval was obtained from İnönü University Clinical Research Ethics Committee and institutional permission was obtained from İnönü University Turgut Özal Medical Center Liver Institute. It will be explained to the parents that not participating in the study will not have a negative effect on the treatment of their children.

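### The visible plan names no actigraphy measure, no deciding day and no designated touch-versus-music test, and has no multiplicity rule, so 5% control of the main conclusion is not shown

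*Protocol*

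**What the plan says.** - **Outcome.** Protocol, Variables of the Study: "Dependent variables: “Actigraphy". This is a device. Its description under Data Collection Tools defines no sleep measure to be analysed.
- **Timing.** Protocol, Data Collection: sleep is recorded the day before the sessions begin, on the day they finish, and on the fourth day afterwards. Neither later day is said to decide.
- **Question.** Protocol, Nursing Initiative: the effects of touch and music "on the sleep of children who have been transferred will be compared".
- **Tests.** Protocol and SAP, Evaluation of Research Data, give the same list: "t-test in independent groups, t-test and ANOVA tests in dependent groups, multiple linear regression and correlation analyzes will be used". One level covers all of them: "Statistical significance level will be accepted as" p<0.05. Sidedness, testing order and adjustment are not mentioned.
- **Covariates.** Protocol, Variables of the Study: "Control variable: Age, gender, height, weight, place of residence, economic status, pain". Whether or how these seven enter the comparison is not stated.
- **Design.** Protocol, Population and Sample: "24 will be included in therapeutic touch groups and 24 in music concert groups". Protocol, Randomization: "Children will be stratified according to their age", in four bands.

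**The concern.** The trial asks one comparative question, but the visible text does not say which single result will answer it. An actigraph can yield more than one sleep measure, there are two later days, and the covariates are open. If the measure or day may be settled after results are seen, or if either day may support the conclusion, a nominal 0.05 per test no longer means a 5% chance of wrongly declaring touch and music different. A reader of the final report also could not tell whether the result shown was the planned one or the most favourable of several.

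**Working it through.** **Plan's own figure.** The only one is the 0.05 level. The plan states no overall error rate that could be reproduced.

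**Inputs from the documents.** 24 per arm (Population and Sample); two later days (Data Collection); 0.05 per test (Evaluation of Research Data).

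**Assumptions.** Normal outcomes, two-sided tests, no true difference between touch and music. The documents give neither the within-child correlation nor the number of measures, so ranges are shown.

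**Step 1: one measure, either later day may decide.** If the two days were independent, 1 − 0.95² = 0.0975. Simulated two-sample t-tests (46 degrees of freedom) for correlated days:

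| Correlation between days | Either day p<0.05 | Both days p<0.05 |
|---|---|---|
| 0 | 9.8% | 0.2% |
| 0.5 | 9.1% | 0.9% |
| 0.7 | 8.3% | 1.6% |
| 0.9 | 7.1% | 2.9% |
| 0.95 | 6.5% | 3.5% |

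An either-day rule exceeds 5%; a both-days rule does not. The text states neither.

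**Step 2: more measures (illustration only).** An assumed 5 measures × 2 days makes 10 tests. If independent, 1 − 0.95¹⁰ = 0.401. With equal correlation among all ten, simulation gives about 29% at 0.5, 21% at 0.7, 13% at 0.9 and 10% at 0.95.

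**Step 3: would a group-by-time test settle it?** Only under sphericity or with a correction. For an uncorrected F test on the three days, 24 per arm, under the null:

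| Pre-to-post correlation | Post-to-post correlation | Error rate |
|---|---|---|
| 0.3 | 0.7 | 5.9% |
| 0.3 | 0.9 | about 7.5% |
| 0.5 | 0.95 | about 7.9% |

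The three days are unevenly spaced around the intervention, so unequal correlations are plausible. A Greenhouse-Geisser correction brings these rates back to about 5%.

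**Step 4: cost of the remedy in detectable difference.** For 80% power, solve P(T > t₁₋α/₂) = 0.80, where T is noncentral t with noncentrality d × √(24/2).

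- Two-sample t, 46 df: d = 0.83 SD at α = 0.05.
- First Holm step of two tests, α = 0.05/2 = 0.025: d = 0.92 SD.
- First Holm step of nine tests (the 10 in the illustration less the primary), α = 0.05/9: d = 1.09 SD.
- Adjusted primary model: df = 48 − 2 arm means − 1 pre-test term − 3 stratum terms = 42; residual SD multiplied by √(1 − ρ²), with no gain credited to the strata. At 0.05, d = 0.83 SD (ρ = 0), 0.79 (0.3), 0.72 (0.5), 0.59 (0.7), where ρ is the assumed pre-post correlation.

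**The case against.** The strongest reply is that the test is less open than it looks. There are two groups, the stated aim is to compare them, and an independent-groups t-test is listed; the dependent-group t-test and ANOVA then naturally describe change across days. That stands, and it is why the point rests on the undesignated measure and day rather than on the lack of any between-arm test. It does not remove the gap, because that t-test could be run on any measure and on either later day.

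Part of the SAP was also not available and could define the outcome. That stands too, and it limits confidence.

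A reader might infer three stronger things that the documents do not support:

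- **That the 5% level is in fact exceeded.** The number of tests that may decide is not stated. A single test on one measure and one day would hold 5%.
- **That the arms will be compared by setting one arm's pre/post p-value against the other's.** No section says so, and a between-arm test is listed. Advising against the practice is reasonable; treating it as planned is not.
- **That the t-test and the regression are interchangeable routes to the conclusion.** Regression is listed without a stated purpose.

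**Conclusion.** The concern holds in limited form. In the visible text no actigraphy measure, deciding day or designated touch-versus-music contrast is named, and no multiplicity rule is given, so control of the main conclusion at 5% is not shown. The figure that needs the fewest assumptions is about 6.5–10% for one measure with either later day allowed to decide (24 per arm, correlation 0.95 to 0). The 10–40% range depends on an assumed five measures and is illustrative; 40% should not be quoted as the trial's error rate, since it also needs ten independent tests. A group-by-time test would be an acceptable alternative only under sphericity or with a correction. The sponsor should make this change. Confidence is medium because part of the SAP could not be seen.

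**What to change.** Before outcomes are compared by group, and with the date recorded, add a paragraph to the protocol and SAP that:

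1. Names one actigraphy measure, one later day and one two-sided 0.05 touch-versus-music contrast.
2. Estimates that contrast with a linear model adjusted for the pre-test value and age stratum (0–1, 2–5, 6–12, 13–18), both already collected.
3. Reports the other measures, the other later day and the within-arm tests as exploratory, with confidence intervals.
4. States that no difference between arms will be inferred from separate within-arm tests.

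**Cost.** No new data are needed. The primary contrast keeps 0.05, and adjustment lowers its detectable difference from 0.83 SD to 0.79–0.59 SD if the pre-post correlation is 0.3–0.7 (assumed), with no gain at 0. Secondary results carry no significance claims. If such claims are wanted, Holm correction applies and tightens with the number of tests: 0.92 SD detectable at the first step of two tests, 1.09 SD at the first step of nine.

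**Timing.** The release is dated 09/09/2021, within the February to October 2021 collection period. If it cannot be shown that the choice was made without sight of results by group, the touch-versus-music comparison must be labelled exploratory.

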## **Evaluation of Research Data**

Percentage, mean, standard deviation, normal distribution, t-test in independent groups, t-test and ANOVA tests in dependent groups, multiple linear regression and correlation analyzes will be used in the evaluation of the data. Statistical significance level will be accepted as  $p < 0.05$ .

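### The plan does not commit the touch-versus-music comparison to adjust for the randomisation age strata or the pre-test actigraphy

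*SAP*

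**What the plan says.** The protocol's Nursing Initiative section states the aim: the effects of therapeutic touch and music "on the sleep of children who have been transferred will be compared".

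Two design features bear on that comparison:

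- **Strata.** The Randomization section says "Children will be stratified according to their age (0-1, 2-5, 6-12, 13-18 years) and randomization with blocks will be made", and aims to equalise group sizes and allocation chances by drawing lots.
- **Pre-test.** Under Data Collection, in both groups "children's sleep will be evaluated with pre-test, post-test and follow-up applications". The actigraphy days are "the day before the application, the day the application ends, and the fourth day after the application".

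The analysis text, under Evaluation of Research Data in the SAP, is a list: "t-test in independent groups, t-test and ANOVA tests in dependent groups, multiple linear regression and correlation analyzes will be used". The protocol section of the same name carries the same list and adds only the software. Neither attaches an outcome, a time point, a covariate or a primary role to any method.

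The Variables of the Study section of the protocol gives "Control variable: Age, gender, height, weight, place of residence, economic status, pain". Age appears there, though not as the randomisation bands. Pre-test sleep does not appear.

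**The concern.** Stratifying the allocation and recording a pre-test gain precision only if the analysis uses them. Nothing in the text requires this for the group comparison. The independent-groups t-test uses neither. The second t-test and the ANOVA are described as being in dependent groups, and whether the ANOVA also has a group factor is not stated.

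Three consequences follow:

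1. **Strata ignored.** When groups are balanced within age bands, between-band variation cancels from the difference in means. It stays in the t-test's standard error, which is then too large, so the test is conservative and loses power.
2. **Pre-test ignored.** The t-test remains valid under randomisation but is less precise than it could be.
3. **Open choice.** With t-test, ANOVA and regression all available and none primary, the analyst can choose between adjusted and unadjusted results after seeing them.

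**Working it through.** **Inputs from the documents.** 24 children per group (protocol, Population and Sample); four age strata (Randomization); significance level 0.05 (SAP), taken as two-sided because sidedness is not stated. The plan gives no power figure to reproduce.

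**Assumed, because the documents are silent.** A true difference of 0.5 SD; the share of outcome variance due to age stratum; the multiple correlation R of pre-test and stratum with the outcome. The last two are shown from zero upward. Errors are normal with total SD 1.

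**Step 1: degrees of freedom.** The t-test has 48 − 2 = 46. Adding three stratum terms and one pre-test slope leaves 42.

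**Step 2: omitting the strata, groups balanced within them.** If stratum explains a share v of the variance, the true variance of the difference is (2/24)(1 − v), while the t-test estimates roughly 2/24. The test statistic therefore has SD of about √(1 − v) instead of 1. Simulation with four strata of 12, split 6:6, 100,000 runs per cell:

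| Age share of variance | 0% | 10% | 25% | 50% | 70% |
|---|---|---|---|---|---|
| Type I error, t-test | 4.9% | 3.9% | 2.4% | 0.5% | 0.03% |
| Type I error, strata in model | 4.9% | 5.0% | 5.0% | 5.1% | 4.9% |
| Power, t-test | 40% | 39% | 38% | 35% | 29% |
| Power, strata in model | 40% | 43% | 50% | 67% | 87% |

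Uneven strata of 20, 14, 8 and 6 give the same power within 1 point.

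**Step 3: groups not balanced within strata.** With 24:24 overall only (40,000 runs), the t-test keeps about 5% type I error. For the same age shares its power is 39 / 40 / 40 / 39 / 38%, against 37 / 41 / 47 / 64 / 85% with strata in the model.

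**Step 4: adding the pre-test.** For ANCOVA the residual SD is √(1 − R²). Power comes from the noncentral t distribution with 42 df and noncentrality 0.5 / (√(2/24) × √(1 − R²)). The 95% CI half-width is 2.018 × 0.2887 × √(1 − R²). The unadjusted t-test has 39.6% power and half-width 2.013 × 0.2887 = 0.58 SD.

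| R | 0 | 0.3 | 0.5 | 0.6 | 0.7 | 0.8 |
|---|---|---|---|---|---|---|
| ANCOVA power | 39.5% | 43% | 50% | 56% | 66% | 81% |
| Half-width (SD) | 0.58 | 0.56 | 0.50 | 0.47 | 0.42 | 0.35 |

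A simulation with a randomly varying pre-test (20,000 runs) is consistent with this: power 38.9% at R = 0, 42.0% at 0.30, 53.4% at 0.57 and 60.8% at 0.66, with type I error of 5.0 to 5.1%.

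**Step 5: choosing afterwards.** Suppose any significant result among the t-test, the stratified model and ANCOVA is accepted. With balanced strata and age shares of 0 to 50%, type I error is about 5.5–5.9%, 6.3–6.8% and 7.7–8.2% for within-stratum pre/post correlations of 0, 0.3 and 0.6.

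**The case against.** The strongest reply is that this is mainly a matter of efficiency. A single unadjusted t-test does not inflate the false-positive rate: it is conservative or close to 5%. The documents also lean towards adjustment. Age is called a control variable, regression is listed, and analyses in dependent groups would use the pre-test in some form. The size of the gain rests on assumed values, and the larger ones (age shares of 50 to 70%, R = 0.8) have no support in the text. The protocol also calls the study quasi-experimental and in places speaks of control and experimental groups, while the arguments above assume stratified random allocation to touch or music. Finally, no ANCOVA can be written until an actigraphy parameter is named.

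Much of this is fair. It limits the point to precision and pre-specification, and the high-end figures should not decide its weight. It does not remove the gap. A listed method and a listed control variable do not say which model compares touch with music, and within-group tests do not make that comparison. The lack of a named parameter is a separate gap that has to be closed first. Part of the SAP text was not available for this check; the protocol's evaluation section repeats the same list and points to no other analysis text.

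**Conclusion.** The concern holds, as something the sponsor should correct. The plan stratifies on age and measures a pre-test but commits neither to the comparison it sets out to make.

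With 24 per group and a 0.5 SD difference, the gain from adjustment ranges from none to large. Power is about 40% unadjusted, 43% to 56% for R between 0.3 and 0.6, and higher only under stronger correlations. If the covariates proved useless, adjustment would cost at most about 1 point of power with balanced strata, and about 2 points for the stratified model without within-stratum balance. Choosing between models after seeing the results would raise type I error modestly, to about 8% in the worst case simulated.

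These sizes rest on the assumed effect, age share and correlations, on normal errors, and on allocation being randomised as the Randomization section describes. The finding that the analysis is not pre-specified depends on none of them.

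**What to change.** Name the actigraphy parameter, then state in the SAP:

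> The primary between-group analysis is an ANCOVA of the post-test actigraphy value (day the application ends) on group, pre-test value and age stratum (0-1, 2-5, 6-12, 13-18). The adjusted touch-minus-music difference is reported with its 95% CI.

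The documents do not say whether post-test or follow-up is primary, so the sponsor should confirm that choice before any outcome data are examined. If both time points are analysed together, use a linear mixed model with group, time, group-by-time interaction, pre-test value and age stratum, and label it secondary. Add pre-test sleep to the control variables, and label the unadjusted t-test as supportive.

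The cost is SAP wording and four degrees of freedom (46 to 42). The data and software stay the same.
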